- Any other condition which, in the opinion of the investigator, would impede compliance or hinder completion of the study, including inability to swallow treatment capsules
- Failure or inability to give informed consent

Sample size / Power:

- Total sample size = 200; 50 per group
- Power = 90%
- Type I error (2-sided) = 5%
- Increase in sample size due to missing data = 10%
- Mean (SD) difference (Vitamin E – Placebo) in relative change [(BL-FU)/BL] in ALT at 24 weeks = 20% (31%)
 - Mean relative change (%) in ALT at 24 weeks in placebo = 20% (based on data from PIVENS trial)
 - Mean relative change (%) in ALT at 24 weeks in Vitamin E = 40% (based on data from PIVENS trial)
- Method of analysis = Williams' test for minimum effective dose

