9 STATISTICAL CONSIDERATIONS

9.1 STATISTICAL HYPOTHESES

- Primary Efficacy Endpoint(s): That one of the doses of vitamin E at 133.4 mg (200 IU), 266.8 mg (400 IU), or 533.6 mg (800 IU) daily is the minimum effective dose for improving relative change in alanine aminotransferase (ALT) from baseline to 24 weeks.
- Secondary Efficacy Endpoints(s): That one or more of vitamin E at 133.4 mg (200 IU), 266.8 mg (400 IU), or 533.6 mg (800 IU) daily is better than placebo in improving:
 - Proportion of patients achieving normalization* of ALT at 24 weeks
 - Mean change in ALT from baseline to 24 weeks
 - Mean change in AST and GGT from baseline to 24 weeks
 - Mean change in hepatic fat determined by FibroScan® CAP score from baseline to 24 weeks
 - Mean change in liver stiffness as assessed by FibroScan® from baseline to 24 weeks
 - Time course and end of treatment improvement in ALT, AST, GGT, and alkaline phosphatase
 - Time course and end of treatment improvement in C-reactive protein (serum marker of inflammation)
 - Time course and end of treatment improvement in change in total cholesterol, LDL cholesterol, HDL cholesterol, and serum triglycerides
 - Changes in fasting glucose levels from baseline to 24 weeks
 - Change in anthropometric measurements (weight, BMI, waist to hip ratio, waist circumference) from baseline to 24 weeks
 - Change in symptom assessment scores from baseline to 24 weeks
 - Change in frequency of CTCAE defined adverse events from baseline to 24 weeks
 - Mean change in ALT from 24 to 48 weeks (post-treatment).

- Mean change in AST and GGT from 24 to 48 weeks (post-treatment).
- Mean change in hepatic fat determined by FibroScan® CAP score from 24 to 48 weeks (post-treatment).
- Mean change in liver stiffness as assessed by FibroScan® from 24 to 48 weeks (post-treatment).

*Normalization of ALT is defined as a decrease in ALT to less than or equal to the ULN at the 24 week visit among participants who had an ALT value greater than ULN at baseline. Values for ULN are defined at each clinical center per institutional guidelines.

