9.2 SAMPLE SIZE DETERMINATION

The primary endpoint is the relative change in ALT at week 24 from baseline [i.e., (ALT at baseline – ALT at week 24)/ALT at baseline]. There are three vitamin E treatment groups: 133.4 mg/day, 266.8 mg/day, 533.6 mg/day and one placebo group. The primary analysis is intention-to-treat analysis of minimum effective dose using Williams' test of mean 24-week relative change in ALT. If the percentage of patients with missing follow-up data on the primary endpoint is greater than 10%, multiple imputation using chained equations method with 50 imputations modeling will be used to impute missing values; otherwise complete-case analysis will be used.

Among patients in PIVENS with baseline ALT ≥ 60 U/L, the mean 24-week relative change in ALT was 40% in the vitamin E (800 IU/day) group and 20% in the Placebo group. The Mean (SD) of the vitamin E – placebo difference in relative change (%) was -20% (31%). Using this estimate as the clinically meaningful difference, the trial has 90% power to detect a significant minimum effective dose given a sample size of 200 patients (50 per group with equal allocation) given a 2-sided Type I error of 5%, missing data rate of 10% and using Williams' test for minimum effective dose (MED) (Williams 1971, Williams 1972) obtained from PASS 2019 software (PASS 2019 Power Analysis and Sample Size Software (2019). NCSS, LLC. Kaysville, Utah, USA, ncss.com/software/pass).

The testing for minimum effective dose starts by comparing the 24-week relative change in ALT in each of the 3 dose groups with the placebo group using critical values obtained from Williams' test for MED. (Critical values will be obtained using SAS PROBMCM function.) Williams' test assumes the same or increasing efficacy with increasing dose; therefore, if the mean change at a dose level is less in absolute value than the mean change in a lower adjacent dose category, the groups are combined for statistical comparison. The lowest dose that is significantly different from placebo is declared the MED. By definition, all doses greater than the MED are also significantly different from placebo.

Sample size estimates for varying sizes of the treatment effect are given below given the same assumptions as above.

24-week relative change in ALT			Sample size	
Vitamin E	Placebo	Vitamin E – Plbo	No. / group	Total
48%	20%	28%	25	100
44%	20%	24%	34	136
40%	20%	20%	50	200
36%	20%	16%	76	304

32%	20%	12%	135	540
28%	20%	8%	303	1212

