9.4.3 ANALYSIS OF THE SECONDARY ENDPOINT(S)

For each secondary endpoint:

- Analyses of secondary endpoints are not dependent on findings of the primary endpoint or on the results of the Williams' test performed on the primary endpoint.
- Analyses will use complete case subjects of the Intention-to-Treat (ITT) Analysis Dataset (i.e., all randomized participants with complete data on each specific secondary endpoint).

The analysis of the 16 secondary endpoints listed in Section 3, Objectives and Endpoints, endpoints will use ANCOVA for continuous endpoints, logistic regression for binary endpoints, and Poisson regression for counts. Complete case analyses will be used for each secondary endpoint, if missing data on that endpoint < 10% and multiple imputation will be used if missing data on the secondary endpoint is 10% or greater. The covariate in the continuous endpoint ANCOVA models will be the baseline value of the continuous endpoint. Sensitivity analyses include use of non-parametric and influence-reducing regression for continuous endpoints (lowess plots and robust regression) and generalized linear models with scale factor estimation to account for under- or over-dispersion for binary endpoint data (dispersion-corrected logistic regression) and count endpoint data (dispersion-corrected negative binomial regression). Each secondary endpoint in the planned table of 16 secondary endpoints will be compared across the 3 vitamin E doses vs Placebo using treatment effect estimates, 95% confidence limits, and p-values. The Benjamini-Hochberg Method will be use to adjust the presented p-values for the false discovery rate (FDR) from the 16x3=48 pairwise p-values.

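### The logistic model for ALT normalization names no baseline covariate, although distance from baseline ALT to the clinic ULN strongly predicts the outcome; the cost is efficiency, not type I error

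*Combined protocol and SAP*

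**What the plan says.** Sections 3 and 9.1 define normalization as week 24 ALT at or below the ULN in participants who were above it at baseline. On the cut-off, 9.1 says "Values for ULN are defined at each clinical center per institutional guidelines".

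For binary and count endpoints, 9.4.3 specifies "logistic regression for binary endpoints, and Poisson regression for counts". It then says "The covariate in the continuous endpoint ANCOVA models will be the baseline value of the continuous endpoint". No covariate is named for the logistic model. The binary sensitivity analysis is a dispersion correction, which does not bring in baseline. Section 9.4.9 compares adjusted with unadjusted models for continuous endpoints only.

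Baseline ALT must be at least 60 U/L (5.1), and values above 400 U/L are excluded (5.2). Each of the 16 secondary endpoints is compared for three doses against placebo, and the 48 p-values are adjusted by Benjamini-Hochberg.

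**The concern.** Normalization is a cut of week 24 ALT at a fixed level, so a participant who starts near the ULN needs a small fall and one who starts far above it needs a very large one. Baseline ALT relative to the ULN is therefore prognostic by construction. The plan adjusts mean change in ALT for baseline but names no adjustment for the cut of the same week 24 value.

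Two things are at stake. One is power in a comparison with about 45 evaluable participants per arm. The other is pre-specification: because 9.4.3 is silent rather than explicit, either model could be fitted after the data are seen, and the choice would feed one endpoint's entries in the 48-p-value table.

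**Working it through.** **Inputs from the documents.** "Total sample size = 200; 50 per group" and "Increase in sample size due to missing data = 10" (%) in the synopsis give 50 × 0.9 = 45 evaluable per arm. Section 9.2 reports that "the mean 24-week relative change in ALT was 40% in the vitamin E (800 IU/day) group and 20% in the Placebo group", with SD 31 points. Baseline ALT runs from 60 to 400 U/L.

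**Inputs the documents do not give (assumed).** ULN of 35 to 60 U/L, fixed or mixed across clinics; baseline ALT log-normal truncated to 60–400 U/L; the distribution of individual relative change, either normal or a log-normal follow-up/baseline ratio.

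**The plan's own figure.** The only stated power is 90% for the primary Williams' test. The standard error is 31 × √(2/45) = 6.54, so the noncentrality is 20/6.54 = 3.06. With a one-sided 5% Williams' critical value of 1.75, power is about Φ(3.06 − 1.75) = Φ(1.31) ≈ 90% (90.4% by noncentral t). So 50 per group reproduces on that basis. The synopsis labels alpha "Type I error (2-sided) = 5"%; at a two-sided critical value near 2.05 the power would be about 84%. That mismatch is separate from this point. The documents state no power for normalization.

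**Why baseline predicts the outcome.** A participant normalizes when the relative fall is at least 1 − ULN/baseline. With an assumed ULN of 45 U/L and normal relative change, P(normalize) = 1 − Φ((required fall − mean)/31), where the mean is 20 on placebo and 40 on vitamin E:

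| Baseline ALT (U/L) | Required fall | Placebo | Vitamin E |
|---|---|---|---|
| 60 | 1 − 45/60 = 25% | 1 − Φ(0.16) = 44% | 1 − Φ(−0.48) = 69% |
| 100 | 1 − 45/100 = 55% | 1 − Φ(1.13) = 13% | 1 − Φ(0.48) = 31% |
| 200 | 1 − 45/200 = 77.5% | 1 − Φ(1.85) = 3% | 1 − Φ(1.21) = 11% |
| 400 | 1 − 45/400 = 89% | 1 − Φ(2.22) = 1% | 1 − Φ(1.57) = 6% |

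Within either arm, moving from 60 to 100 U/L changes the probability by more than the treatment effect does at either of those baselines.

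**Power with and without the covariate.** Two-arm trials were simulated (one dose against placebo, Wald test, two-sided 5%, no multiplicity adjustment). With a single ULN, log baseline ALT and log(baseline ALT/ULN) give the same test, because log ULN is a constant. Medians and log SDs below are for baseline ALT before truncation.

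| Error model | ULN and baseline ALT | n per arm | Unadjusted | Adjusted | Gain (points) |
|---|---|---|---|---|---|
| Normal change | ULN 40, median 90 | 45 | 50.3% | 52.0% | 1.7 |
| Normal change | ULN mixed, median 100 | 45 | 45.8% | 51.0% | 5.2 |
| Log-normal ratio | ULN 35, median 80, log SD 0.25 | 45 | 79.1% | 81.6% | 2.5 |
| Log-normal ratio | ULN 55, median 80, log SD 0.4 | 45 | 68.0% | 77.5% | 9.5 |
| Log-normal ratio | ULN 40, median 100, log SD 0.5 | 45 | 58.7% | 67.9% | 9.2 |
| Log-normal ratio | ULN 55, median 100, log SD 0.5 | 50 | 68.0% | 81.0% | 13.0 |
| Log-normal ratio | ULN mixed 35–60, median 90, log SD 0.5 | 45 | 62.7% | 76.1% | 13.4 |

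Across independent sets of runs with the plan's effect and SD, the gain was 1 to 9 points with a normal relative change (1 to 5 for a ULN of 35 to 45 in one set) and 2.5 to about 14 points with a log-normal ratio. With mixed ULNs and a log-normal ratio, log baseline alone gained 7.3 to 9.8 points and log(baseline/ULN) gained 9.7 to 13.4, which is why the ratio is the better covariate.

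A generic latent-variable model, which takes assumed response rates instead of the plan's SD, shows what drives the size. With a baseline/week 24 correlation of 0.3 the gain is about 1 to 4 points; with 0.7 it is about 13 to 17. The documents give no such correlation.

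**Null.** With no treatment effect, rejection was 4.0% and 4.2% for the two logistic tests.

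**The case against.** The strongest reply is that 9.4.3 does not forbid covariates in the logistic model; it is silent. That stands: an unadjusted model is the natural reading, not a stated rule. It is still a reason to write the model down.

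The endpoint is also one of 16 secondaries, without a power claim, and its p-values go through Benjamini-Hochberg. That stands too. The powers above use an unadjusted 5%, so absolute power under the plan's rule would generally be lower.

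Several stronger readings are tempting, and the documents do not support them:

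- A reader might infer a guaranteed loss of at least 6 points. Gains of 2 to 5 points arise under plausible assumptions, and nothing in the documents selects among them.
- A reader might infer that chance imbalance in clinic ULN drives the comparison. Section 6.3 stratifies randomization by clinical center with permuted blocks, so a ULN set by center is largely balanced by design. Baseline ALT itself is not a stratification factor.
- A reader might infer that the doses could spuriously appear to differ because of where participants started. Null rejection near 4% for both models shows that error is controlled.
- A reader might infer that cutting ALT discards the information, and that normalization should give way to the full-scale analysis. ALT is already analysed continuously, as the primary endpoint and as a secondary with baseline adjustment. The cost of the cut is a different quantity from the cost of the missing covariate, and the gains above measure only the latter.

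**Conclusion.** The concern holds as a minor gap in efficiency and pre-specification. Read as written, 9.4.3 leaves the normalization model without baseline ALT, a strong predictor by construction. Adjustment raised power in every scenario run, by about 1 to 14 points under the plan's effect (20% against 40%, SD 31%) with 45 to 50 per arm. The direction is consistent; the size is not a property of this trial that can be read from the documents, because it depends on the baseline ALT distribution, the clinic ULNs and the error model. Type I error and the primary dose-finding conclusion are unaffected.

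**What to change.** In 9.4.3, state that the logistic model for ALT normalization includes log(baseline ALT / clinic ULN) as a covariate. Because the adjusted odds ratio is conditional on that covariate, also state that the standardized difference in normalization proportions (model predictions averaged over the trial population) will be reported for each dose against placebo with a 95% CI.

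The cost is one or two sentences. Baseline ALT is already collected, and each clinic's ULN is already needed to define the endpoint. Sample size, visits and the primary analysis do not change. The text should be settled before unmasking.

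### The dispersion-corrected logistic regression planned as a sensitivity analysis for ALT normalization cannot measure dispersion in one yes/no result per participant

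*Combined protocol and SAP*

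**What the plan says.** Section 9.4.3 of the combined protocol and SAP assigns "logistic regression for binary endpoints, and Poisson regression for counts". For the sensitivity analyses it adds "generalized linear models with scale factor estimation to account for under- or over-dispersion for binary endpoint data (dispersion-corrected logistic regression"), followed by a parallel provision for counts.

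The secondary endpoint this serves is listed in sections 3 and 9.1 as "Proportion of patients achieving normalization* of ALT at 24 weeks". The footnote defines normalization as "a decrease in ALT to less than or equal to the ULN at the 24 week visit among participants" whose baseline value was above the ULN, and leaves the ULN to each clinical center. Each participant therefore gives one yes or one no, at one visit.

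The only covariate stated in section 9.4.3 is for a different model: "The covariate in the continuous endpoint ANCOVA models will be the baseline value of the continuous endpoint". For the logistic model the section names no covariate, no clinic term and no grouping of participants into cells. It also does not say whether the scale factor comes from the Pearson statistic or from the deviance. Section 6.3 stratifies randomization by clinical center.

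**The concern.** A single yes/no outcome with probability p has variance p(1-p). Once the mean is fitted, no second quantity is left to estimate, so over- or under-dispersion means something only when outcomes are grouped into cells with denominators above 1. On individual data, software still prints a scale factor, but it does not measure lack of fit.

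Two things are at stake. A report could state that the normalization result was robust to over-dispersion when the algebra guaranteed that finding. And because the estimator is left open, the analyst's choice decides whether the check is empty or shifts the false-positive rate for reasons unrelated to model adequacy. The check would also miss the most plausible source of heterogeneity, which is clinic: each center sets its own ULN, and so its own threshold for the endpoint.

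**Working it through.** The documents give no figure for the dispersion analysis, so there is none to reproduce.

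**Inputs.**
- Section 1.1: "Total sample size = 200; 50 per group", in four arms.
- Section 9.2: "missing data rate of 10"%, so 200 × 0.9 = 180 evaluable, or 45 per arm.
- Nominal error of 5%, two-sided, as in section 9.2 ("given a 2-sided Type I error of 5"%).
- Model: arm only, 4 parameters, individual 0/1 data. This is inferred from the endpoint definition and from the absence of any stated covariate or grouping.
- Normalization rate: not given. I assume a common rate in all arms, from 10% to 50%.

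**Pearson scaling.** Take an arm with n participants and observed proportion p strictly between 0 and 1. Each of the np responders contributes (1-p)²/[p(1-p)] = (1-p)/p. Each of the n(1-p) non-responders contributes p/(1-p). The arm total is n(1-p) + np = n. Summed over arms, the Pearson statistic is N, so the factor is N/(N-4).
- N = 200: 200/196 = 1.0204, and each SE is multiplied by √1.0204 = 1.010.
- N = 180: 180/176 = 1.0227, and each SE is multiplied by 1.011.

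The corresponding asymptotic error is 2[1 - Φ(1.96 × 1.010)] = 4.8%. Simulated fits with a strong clinic effect (SD 1 on the logit scale) still gave 1.0204, with no variation, at rates of 20% and 40%.

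**Deviance scaling.** On individual data the saturated log-likelihood is zero. At a common rate p the factor is therefore approximately -2[p ln p + (1-p) ln(1-p)] × N/(N-4), a function of the rate alone. At p = 10% and N = 200 it is 0.650 × 1.0204 = 0.663, so each SE is multiplied by √0.663 = 0.815.

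The error columns below come from 400,000 simulated null trials per rate, 50 per arm, for one dose against placebo. They use Wald tests at 1.96 and count comparisons with an empty arm as non-significant.

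| Assumed rate | Deviance factor (N = 200) | SE multiplier | Error, deviance-scaled | Error, ordinary logistic |
|---|---|---|---|---|
| 10% | 0.663 | 0.815 | 9.8% | 2.4% |
| 15% | 0.863 | 0.929 | 6.7% | 4.1% |
| 20% | 1.021 | 1.011 | 4.8% | 4.3% |
| 30% | 1.247 | 1.117 | 2.9% | 4.5% |
| 50% | 1.415 | 1.189 | 2.1% | 5.7% |

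The factor crosses 1 at a rate of 19% to 20%. Below that, scaling shrinks the standard errors; above it, scaling inflates them. At a 10% rate, about 7% of null comparisons pass from non-significant to significant through the scaling alone.

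**The case against.** The strongest objection is that the layout and the estimator are unstated, and silence is not a specification. If participants were grouped by clinic and arm (9 × 4 = 36 cells, 200/36 ≈ 5.6 per cell), a factor could be estimated. With an assumed clinic SD of 1 on the logit scale it averaged about 1.5 to 1.8 in simulation. This stands as a limit: the defect belongs to the analysis as described, not to every analysis the wording could cover. It does not rescue the plan, which states no grouping. Because arms are balanced within clinic, that grouped correction also made the test conservative, with about 1% error under the same assumption.

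The constant Pearson factor has limits as well. It needs both outcomes present in every arm; at a 10% rate some arm has no responder in about 2% of trials. It also needs arm to be the only term. With a baseline covariate added and a 20% rate, the factor ranged from about 0.95 to 1.10 (5th to 95th percentile). That spread is chance and not dispersion.

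A reader might infer that the trial's false-positive rate is inflated, or that a null normalization result could be reported as significant. The documents do not support that. Inflation needs deviance scaling together with a common rate below about 20%, and neither is stated. The factor also pools all four arms: assumed rates of 10% on placebo and 30% on each dose give (0.650 + 3 × 1.222)/4 × 1.0204 = 1.10, which widens the standard error. No rule lets a sensitivity p-value replace the main one.

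Nor is this shown to be the only robustness check for the endpoint. Section 9.4.3 says only that sensitivity analyses include it, the same section has a multiple-imputation rule for missing data, and section 9.4.7 lists exploratory effects by clinic.

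**Conclusion.** The point holds for the model that section 9.4.3 describes: one yes/no per participant, with no stated grouping or covariate. There the planned scale factor cannot do what it is said to do. Under Pearson scaling it adds about 1% to every standard error and carries no information, not even about clinic differences. Under deviance scaling it moves the error of a nominal 5% test to anywhere from about 9.8% (10% rate) to 2.1% (50% rate), with almost no distortion near 20%. Those figures rest on an assumed common rate, 50 evaluable per arm and an arm-only model.

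The severity is minor. One of 16 secondary endpoints is touched (3 of the 48 pairwise p-values), and only in a sensitivity analysis. The main logistic regression, the primary endpoint, the sample size and the minimum-effective-dose procedure are unaffected. The dispersion provision for count endpoints is sound, because over-dispersion is meaningful there.

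**What to change.** In section 9.4.3, delete scale-factor estimation for binary data and keep it for counts. In its place, specify a logistic regression of ALT normalization on treatment arm, stratified by or adjusted for clinic. Clinic is the randomization stratum and the level at which the ULN is set, so this check can differ from the main result for an interpretable reason.

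The cost is one sentence of wording and standard software, with no change to data collection or sample size. The downside is sparse strata: about 22 participants per clinic over four arms leaves five or six per cell, and a clinic in which nobody or everybody normalizes adds nothing to a stratified estimate.

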3 OBJECTIVES AND ENDPOINTS

OBJECTIVES	ENDPOINTS	JUSTIFICATION FOR ENDPOINTS
Primary		
The primary objective is to determine the minimum effective dose of vitamin E (133.4 mg, 266.8 mg, or 533.6 mg) at which measures of NAFLD are improved	Relative change in ALT at week 24 from baseline [i.e., (ALT at baseline – ALT at week 24)/ ALT at baseline]	ALT is the most accepted short term (<12 months) surrogate marker for histologic improvement in NAFLD.
Secondary		
The secondary objectives have been selected to provide further information on the minimum effective dose of vitamin E needed to improve measures of NAFLD progression, and to provide information on the post-treatment effects of vitamin E on the liver.	Proportion of patients achieving normalization* of ALT at 24 weeks Mean change in ALT from baseline to 24 weeks Mean change in AST and GGT from baseline to 24 weeks Mean change in hepatic fat determined by FibroScan® CAP score from baseline to 24 weeks Mean change in liver stiffness as assessed by FibroScan® from baseline to 24 weeks Time course and end of treatment improvement in ALT, AST, GGT, and alkaline phosphatase Time course and end of treatment improvement in C-reactive protein (serum marker of inflammation)	These endpoints were selected because they measure important co-morbidities of NAFLD and are useful for determining if vitamin E improves other features commonly associated with NAFLD. Safety and quality of life outcomes are also included.

OBJECTIVES	ENDPOINTS	JUSTIFICATION FOR ENDPOINTS
	
Time course and end of treatment improvement in change in total cholesterol, LDL cholesterol, HDL cholesterol, and serum triglycerides
 
Changes in fasting glucose levels from baseline to 24 weeks
 
Change in anthropometric measurements (weight, BMI, waist to hip ratio, waist circumference) from baseline to 24 weeks
 
Change in symptom assessment scores from baseline to 24 weeks
 
Change in frequency of CTCAE defined adverse events from baseline to 24 weeks
 
Mean change in ALT from 24 to 48 weeks (post-treatment).
 
Mean change in AST and GGT from 24 to 48 weeks (post-treatment).
 
Mean change in hepatic fat determined by FibroScan® CAP score from 24 to 48 weeks (post-treatment).
 
Mean change in liver stiffness as assessed by FibroScan® from 24 to 48 weeks (post-treatment).
	
Tertiary/Exploratory		

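### Adverse-event frequency is listed as an efficacy hypothesis and FDR-adjusted with 45 other comparisons, which lowers the power to flag a moderate harm

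*Combined protocol and SAP*

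**What the plan says.** Section 9.1 states one hypothesis for all secondary efficacy endpoints, that one or more of the three doses "daily is better than placebo in improving" each listed item. The twelfth of the 16 items is "Change in frequency of CTCAE defined adverse events from baseline to 24 weeks". The justification column of the section 3 table recognises that the list is mixed: "Safety and quality of life outcomes are also included".

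Section 9.4.3 treats all 16 items alike. Each is "compared across the 3 vitamin E doses vs Placebo using treatment effect estimates, 95% confidence limits, and p-values", using ANCOVA for continuous endpoints and "logistic regression for binary endpoints, and Poisson regression for counts". The p-values then go through a single adjustment: "The Benjamini-Hochberg Method will be use to adjust the presented p-values for the false discovery rate (FDR) from the 16x3=48 pairwise p-values". No endpoint is exempted. The FDR level is not given, and no adjustment of the confidence limits is stated.

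Section 9.4.4 separately plans by-group tables of any adverse event, number of events and highest severity, with Fisher's exact p-values and no stated multiplicity adjustment. The only recipient it names is the DSMB, during the trial. Section 9.3 defines a Safety Analysis Dataset, but section 9.4.3 analyses its endpoints in the ITT set.

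**The concern.** For adverse events the question is whether a dose is worse than placebo. FDR control limits false positive claims, which is reasonable for a long list of possible benefits. For a harm the costlier error is the missed signal, and the adjustment makes that error more likely.

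It also ties the safety reading to unrelated results. The same adverse-event data could be flagged or not according to how CAP, lipids or waist circumference turn out.

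This bears on the trial's purpose. Section 2.3.3 argues that finding a lower effective dose is valuable because long-term adverse effects might then be avoided, so adverse-event frequency by dose is the other half of that argument.

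**Working it through.** **Family size.** Counting the items in section 9.1 gives 16, and 16 × 3 = 48, which reproduces the plan's figure. One item is adverse-event frequency, so 1 × 3 = 3 contrasts are adverse-event contrasts and 48 − 3 = 45 are not.

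**Cut-off for an adverse-event p-value.** Under Benjamini-Hochberg with k rejections in all, a p-value is rejected if it is at most k × q/48. With q = 0.05 (assumed):

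| Total rejections k | Cut-off | Two-sided z |
|---|---|---|
| 1 (the adverse-event test alone) | 0.00104 | 3.279 |
| 6 | 0.0063 | 2.734 |
| 15 | 0.0156 | 2.418 |
| 48 | 0.05 | 1.960 |

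**Power for one contrast, by hand.** Inputs are 50 per arm (section 9.2), Poisson counts (section 9.4.3), a two-sided test (stated for the primary endpoint, assumed here) and assumed event rates. With placebo rate λ and rate ratio RR:

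SE = √[1/(50λ) + 1/(50λ·RR)], power ≈ Φ(ln RR/SE − z)

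For λ = 1 and RR = 1.5, expected counts are 50 and 75. SE = √(1/50 + 1/75) = 0.1826, and 0.4055/0.1826 = 2.221.

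- Unadjusted: Φ(2.221 − 1.960) = 0.60
- k = 6: Φ(2.221 − 2.734) = 0.30
- k = 15: Φ(2.221 − 2.418) = 0.42
- Strictest step: Φ(2.221 − 3.279) = 0.145

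**Power under the whole 48-test procedure, by simulation.** The three adverse-event contrasts share the placebo arm, and the other endpoints are independent of each other. The excess is on the top dose only. The Benjamini-Hochberg range runs from no efficacy endpoint active to eight active at all doses, where an active endpoint has an effect of 20/31 = 0.65 SD, the primary planning value in section 9.2.

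| Placebo events per person | RR | Unadjusted | Inside the 48-test family |
|---|---|---|---|
| 1 | 1.5 | 61% | 14–47% |
| 0.25 | 2 | 53% | 6–37% |
| 0.5 | 2 | 83% | 32–72% |
| 2 | 1.5 | 88% | 45–81% |
| 0.25 | 3 | 95% | 56–90% |
| 1 | 2 | 98% | 80–97% |

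In the second row the hand formula gives 52% unadjusted and 10% at the strictest step. The simulated 6% is lower because the expected placebo count is only 12.5.

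**All doses affected.** If all three doses carry RR 1.5 at 1 event per person, the chance of flagging at least one contrast is 84% unadjusted and 30–72% inside the family.

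**Share due to trial size.** In the first two rows even the unadjusted test misses 39% and 47% of the time. Removing the adjustment cannot recover that part.

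**The case against.** The strongest case on the other side is that the plan already contains most of what is needed. Section 9.4.3 gives an effect estimate and 95% confidence limits for each dose against placebo. The FDR step is applied to the presented p-values only, so an apparently unadjusted interval for the adverse-event rate ratio is already planned. Section 9.4.4 adds Fisher p-values with no stated adjustment, and section 8.3.5 gives the DSMB comparisons of adverse-event rates by treatment group. A two-sided test also detects an excess, whatever the wording of the 9.1 heading.

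These points narrow the concern but do not remove it. Section 9.4.4 does not say that its tables enter the final report, and it plans no dose-versus-placebo estimate or interval. The secondary endpoint table would still show an FDR-raised p-value for adverse events among the efficacy rows. The plan would then hold an adjusted and an unadjusted analysis of adverse events with no rule on which governs.

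A reader might go further and infer that a relevant harm would usually come out non-significant and be read as no difference. The documents do not support that. 'Usually' fails for the larger harms in the table above. For intermediate harms the answer depends on how many efficacy endpoints are positive. Nothing in the plan says that a non-significant adverse-event p-value will be taken as evidence of safety.

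**Conclusion.** The point stands in a limited form. Adverse-event frequency is framed as a benefit hypothesis, and its three p-values are adjusted with 45 others. This always costs power to flag an excess and makes the result depend on the efficacy findings. The loss matters most for moderate harms, where power of about 53–61% unadjusted falls to 6–47%. For large harms it is smaller, with 56–97% remaining.

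The event rates, the 5% FDR level, two-sided testing of secondary endpoints and independence among the other endpoints are assumptions, and the first two have no figure anywhere in the documents. The direction of the effect needs none of them, because a Benjamini-Hochberg adjusted p-value is never smaller than the raw one.

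**What to change.** 1. Remove adverse-event frequency from the efficacy list in section 9.1, and reconcile section 3 with that change.
2. Take its three contrasts out of the Benjamini-Hochberg family, and restate the family as 15 × 3 = 45.
3. Report adverse-event frequency under section 9.4.4, in the Safety Analysis Dataset, as a rate ratio or rate difference for each dose against placebo with an unadjusted 95% confidence interval. State that this goes into the final report as well as to the DSMB.
4. Add a sentence that a non-significant difference in adverse events will not be interpreted as evidence of no harm.

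The cost is a change of wording and one table row moved, with no new data. The downside is that more chance adverse-event signals will be flagged, which is the safer error for a harm endpoint. The change does not make up for the trial's limited size, so the width of the intervals should carry the safety message.
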